Cystic fibrosis (CF) is an autosomal recessive disorder, caused by mutations to the cystic fibrosis transmembrane conductance regulator (CFTR) gene encoding for the CFTR protein. CF affects around 10,000 people in the UK with a life expectancy of 49 years in 2019.¹ Although CF is a multi-system disorder, its impact on the respiratory track and gastrointestinal (GI) system are of particular clinical importance.² In the gut, CFTR mutations result in pancreatic exocrine insufficiency in around 85% infants resulting in maldigestion and impaired nutrition,³ with adequate nutrition in CF linked to life expectancy.⁴ Due to the success of the newborn screening programme in the UK most people with CF (pwCF) are now identified within the first few weeks of life and commenced on pancreatic enzyme replacement therapy (PERT). Cystic fibrosis has a high associated treatment burden, with PERT in particular contributing to this, with patients often have to take 25-30 capsules per day.⁵ However, despite this almost all pwCF experience GI symptoms including abdominal pain, flatulence, constipation and bloating,⁶ with two thirds missing work or school because of this.⁷ This is why ‘How can we relieve gastro-intestinal symptoms, such as stomach pain, bloating and nausea in people with Cystic Fibrosis?’ was identified as one of the top 10 research priorities in a James Lind Alliance Priority Setting Partnership (JLA PSP) in CF conducted by our group.⁸

In addition, other GI manifestations affecting pwCF include distal intestinal obstructive syndrome (DIOS), CF related liver disease (CFRD) and pancreatitis. DIOS is a severe GI complication in CF defined as a complete intestinal obstruction with an ileo-caecal mass and abdominal distension, thought to result from the accumulation of faecal material at the ileo-caecal valve.⁹ It affected 5.7% pwCF in the UK (2.5% in <16 years and 7.7% in adults)¹ and 2.1% in the US (<18 years 1.7%, adult 2.4%)¹⁰ in 2019. However, the pathology underlying DIOS and GI symptoms are currently not well understood.

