DURATION OF THE STUDY AND PARTICIPANT INVOLVEMENT

Registry database Duration: 24 months

Participant Duration: This is a registry study therefore no individual participant interaction. However, registry data from the US and UK CF registries will be used from 2007 to 2017.

End of the registry study

Data will be destroyed in line with the UK and US CF registry requirements at the end of the study period. A detailed description of this is outlined in the data management plan. The end of the study will be 31/09/2023.

SELECTION AND WITHDRAWAL OF PARTICIPANTS

Recruitment

This is a registry study using data from 2007-2017 from the UK and US CF registries. As such no individual participants will be recruited to the study. PwCF have given explicit consent to their usual CF teams for their demographic, clinical care, and health outcomes data to be submitted to either the UK or US CF registries.

Eligibility criteria

Inclusion criteria

All CF patients of any genotype who are registered on the UK or US CF registries from 2007-2017 will be included.

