4.2.2 Exclusion criteria

Patients whose CFTR modulator status is unknown or only have one year of CFTR data recorded on the registry will be excluded from the analysis of the effects of CFTR modulators. This is to account for the fact that DIOS data is annualised on the registry, therefore there is no certainty at what time of year DIOS was diagnosed in relation to commencing CFTR modulatory therapy.

Expected duration of participant participation

No individual participant interaction. The CFTR MAGIC study will take place over 24 months, from 1/10/2021 to 30/9/2023.

Participant Withdrawal

Not applicable – no individual participant involvement.

Informed consent

PwCF have given explicit consent to their usual CF teams for their demographic, clinical care, and health outcomes data to be submitted to either the UK or US CF registries.^{15, 16} Written consent is gained from pwCF or their parent/ legal guardian and as part of this they are made aware that the information may be used for research and to plan and improve the quality of clinical care. For the UK CF Trust the use of any data from the registry requires the approval of the Registry Steering Committee.¹⁵ In the US, the request for registry data is reviewed and approved by the Patient Registry/Comparative Effectiveness Research Committee. The project has received approval from both the US and UK registries for patient data to be released to be used for this project. Data is released by the registries as anonymised forms of the data to maintain patient confidentiality. Additional patient specific consent for CFTR MAGIC is therefore not required.

DATA COLLECTION REGIMEN

No new data collection will be necessary within this project. Existing data will be provided by the US and UK CF registries. Requests for the data was approved by the UK CF Trust Registry Steering Committee after reviewing the programme development grant aims, statistical analysis and plan for publication of results. In the US, the request for registry data was reviewed and approved by the Patient Registry/Comparative Effectiveness Research Committee and was subject to peer review. Data will be provided as anonymised data so the individuals cannot be identified and analysed using Stata software.

ACCESS TO REGISTRY DATA

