Hypothesis 2b will be explored in the US population only given that introduction of Orkambi was delayed in the UK until 2019.

ITS will explore proportion of DIOS events at population level in the CFTR modulator population and the propensity score defined comparator population. ITS will explore proportion of overall PERT usage (user/non user), and the proportion of individuals with a reduction in weight standardised PERT dose (decrease/no decrease)

- Sensitivity will include distributed lag of 1-3 (years) to account for the possibility that exposure time in the first year was not sufficient for a change in outcome, compared to non-lagged, and to explore PERT usage status change to non-user.
- Autoregression will be visually assessed and effects will also be compared with those from autoregressive model (Prais-Winsten).

Analysis will be performed overall and stratified by 1) Age group (<6, 6-11, 12+) to account for clinical distinctions in pre-schoolers, school age children and adults, 2) History of meconium ileus, as these individuals are at higher risk of DIOS events.

Analysis of hypothesis 2a: Controlled interrupted time series: ivacaftor analysis in G551D criteria

- Segmented regression (with and without lag term), and Prais-Winsten regression for serial correlation.
- Impact model: downward trend (no/minimal level change)
- Model includes: pre intervention, level change, post intervention: interaction with covariates (age, gender, disease status).
 - Pre intervention: no CFTR modulator (time control)
 - Post intervention: ivacaftor (minimum 6 months)
 - US 2007-2011:2012-2017
 - UK 2007-2011:2012-2017
- Propensity score matched controls (demographic control)

Analysis hypothesis 2b. Interrupted time series: lumacaftor/ivacaftor analysis in US F508del subgroup.

- Hypothesis, downward trend no lag.
- Pre intervention no CFTR modulator: (time control)
- Post intervention: lumacaftor/ivacaftor, minimum 6 months
 - US 2007-2014:2015-2017
- Propensity score matched controls (demographic control)

- Parallel plot of UK F508del homozygous subgroup (indirect genotype control)

Objective 3: Determine the effect of CFTR modulators on DIOS and PERT: patient-level time series

This will focus on patient level associations to complement the registry level findings. We will specify explore associations in the incidence of PERT usage and DIOS events between 2012 and 2017 in individuals with CFTR modulators, compared to propensity matched controls.

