- UK 2012-2017 & US 2012-2017 separately
 - Exposure: ivacaftor (minimum 6 months) vs No modulator (matched)
 - Secondary comparator: ivacaftor alone and lumacaftor/ivacaftor (US only)
- DIOS events:
 - Outcome: Patient-level annualised DIOS event counts
 - Multilevel Poisson Regression model for count data (or negative binomial) by year
 - Incidence rate ratio (frequency of DIOS events)
 - Adjusted analysis for main covariates (DAG – Fig 2), also include history of DIOS as pre-exposure time will not be modelled.
 - Contingency table with χ^2 /fisher if insufficient events for modelling.
- PERT usage:
 - Outcome: Patient-level annualised PERT dosage standardised by weight
 - Secondary: decreased PERT usage vs continued/increased
 - Multilevel linear regression for continuous data
 - Secondary: multilevel logistic regression for dichotomised data
 - Adjusted for main covariates (DAG – Fig 2), also include history of DIOS as pre-exposure time will not be modelled.
- Sensitivity analyses
 - CFTR modulator start year excluded, finite distributed lag (1-3 years).
 - Long run propensity (cumulative 0-3 years), cumulative modulator exposure.

Sample size and justification

N/A.- registry study

ADVERSE EVENTS

This is a registry study therefore there is no individual participant interaction and as such no associated risk or burden for participants in the study. Patient's data will be provided as anonymised data and therefore patient confidentiality will be maintained.

ETHICAL AND REGULATORY ASPECTS

ETHICS COMMITTEE AND REGULATORY APPROVALS

Requests for the data required the approval of the UK CF Trust Registry Steering Committee after reviewing of the programme development grant aims, analysis and plan for publication of results. In the US, the request for registry data was reviewed and approved by the Patient Registry/Comparative Effectiveness Research Committee and was subject to peer review.

The data will be provided from the registries as anonymised data so the individuals cannot be identified. Specifically, the CF Foundation requires that no individually identifiable information from the CF Foundation Patient Registry shall be included in publications and other written products and data must be presented in the aggregate. Both US and UK registries require that all tables or presentation of the data generated from registry data should include a patient count of five or more in each cell and any values less than 5 should be represented as <5.

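### Every PERT dose outcome with a stated scale is per kg, so extra weight gain on modulators can read as reduced PERT use; never-users also sit in the decrease outcome as worded

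*Combined protocol and SAP*

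**What the plan says.** The PERT outcomes are set out in the Statistical Analysis section.

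- Objective 2, status: "ITS will explore proportion of overall PERT usage (user/non user".
- Objective 2, dose: "the proportion of individuals with a reduction in weight standardised PERT dose (decrease/no decrease". No minimum change, reference year or user-only denominator is given.
- Objective 3, main: "Outcome: Patient-level annualised PERT dosage standardised by weight", analysed as a continuous variable.
- Objective 3, binary: "Secondary: decreased PERT usage vs continued/increased". This line does not repeat the weight standardisation, and it leaves patients never on PERT without a category.

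The population is broad: "All CF patients of any genotype who are registered on the UK or US CF registries from 2007-2017 will be included". For the modulator analyses, "Patients whose CFTR modulator status is unknown or only have one year of CFTR data recorded on the registry will be excluded"; PERT non-users are not removed. The Background states "pancreatic exocrine insufficiency in around 85% infants", and it describes treatment burden in absolute terms: "patients often have to take 25-30 capsules per day".

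Controls are patients not eligible for the modulator and not taking it, matched 3:1 on a propensity score built from pre-exposure information. Objective 3 states that pre-exposure time is not modelled.

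**The concern.** Dose per kg is a ratio, and its denominator can respond to the treatment under study. If modulator patients gain more weight than their controls after the index year, the ratio falls while the prescription and the capsules taken stay the same. Both the Objective 2 decrease outcome and the Objective 3 continuous outcome move in the hypothesised direction, and no planned dose outcome would show that intake had not changed. If change is measured from a fixed baseline year, gain that builds up over several years would also resemble the gradual downward trend in the plan's impact model.

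The second problem is the denominator of the decrease outcome. A patient who has never taken PERT cannot reduce it. If such patients are counted as no decrease, they add no information, and their share may differ between modulator patients and controls of non-eligible genotype.

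At stake is whether a finding of reduced PERT use can be told apart from weight gain or, in Objective 3, from a difference in the mix of users.

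**Working it through.** The plan states no sample size, effect size or expected proportion for PERT, so there is no figure of its own to reproduce. All rates below that are not attributed to the documents are assumptions.

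**1. Weight gain at constant intake.** If weight rises by a fraction g and total dose is fixed, dose per kg falls by g/(1+g).

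- g = 3%: 0.03/1.03 = 2.9%
- g = 5%: 0.05/1.05 = 4.8%
- g = 10% (20 to 22 kg): 0.10/1.10 = 9.1%

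These are the shifts that would appear in the continuous Objective 3 outcome. With no minimum change stated, each is also a decrease in the binary outcome.

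**2. Effect on the binary outcome.** Take g as the gain beyond that of controls. Let the yearly log change in dose per kg be normal with mean 0 in controls and -log(1+g) in exposed patients, with SD s. Then P(decrease) = Φ(log(1+g)/s), which is 50% at g = 0.

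| Extra gain g (assumed) | s = 0.10 | s = 0.20 |
|---|---|---|
| 3% (log 1.03 = 0.0296) | Φ(0.296) = 62% | Φ(0.148) = 56% |
| 5% (log 1.05 = 0.0488) | Φ(0.488) = 69% | Φ(0.244) = 60% |

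Intake is unchanged throughout.

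**3. Check under a different model.** A simulation of 1,000,000 patients assumed that half have an unchanged dose, the rest have a log-dose change with SD 0.15, and log-weight change has SD 0.05. Mean log-weight gain was raised from 0 to 0.05 (about 5%):

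- any fall in dose per kg: 50% to 73%
- fall of at least 10%: 13.5% to 24.9%
- fall of at least 20%: 3.9% to 6.8%
- fall in absolute dose: 25% in both cases

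With no patients, or 80% of patients, on an unchanged dose, the first figure becomes 62% or 80%. A minimum-change threshold shrinks the artefact without removing it. Absolute dose is unaffected.

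**4. Never-users.** If a share q of an arm are never-users coded as no decrease, P(decrease, all) = (1-q) × P(decrease, users).

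- Equal shares: q = 15% carries over the Background's infant figure (100% - 85%), which is an assumption. With 30% versus 45% of users decreasing, the arms read 25.5% versus 38.25%. The difference falls from 15.0 to 12.75 points and the risk ratio stays at 1.50. At q = 10% and 50% the difference is 13.5 and 7.5 points.
- Unequal but stable shares, Objective 2: with 30% of users decreasing throughout and q = 30% (exposed) and 15% (control), the series read 21% before and after in one arm and 25.5% before and after in the other. Level change and slope change are both zero.
- Unequal shares, Objective 3: the same inputs give 21% versus 25.5%, a difference of -4.5 points with no effect among users. There is no modelled pre-exposure period to absorb it. Reversing the shares gives +4.5 points.

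**The case against.** Several counter-arguments carry weight.

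- **Ordinary growth is largely handled.** A child going from 20 to 22 kg occurs in both arms. Matched controls, the pre-intervention trend and the age strata deal with growth common to both. This stands: only gain in excess of controls matters. Matching on pre-exposure characteristics cannot remove gain that arises after exposure.
- **The documents do not show that extra gain occurs.** They give no figure for it. This stands, so the size is conditional.
- **The wording is partly silent.** Counting any fall, among everyone, follows from the absence of a threshold and of a user restriction; the plan does not state either as a rule. In Objective 3 the word for continued use suggests current users. This stands, and makes Objective 3's binary outcome the less certain case.
- **Dose per kg is a legitimate scale** in a cohort running from under 6 years to adults, and user/non-user status is analysed separately and is untouched by weight. Both points stand. They are reasons to keep these outcomes, but they do not supply a measure of intake.
- **Matching may already balance PERT.** It uses all pre-exposure information and PERT is a requested variable. That is possible, but PERT and pancreatic status are not in the listed demographics.

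A reader might infer that a different share of non-users could by itself produce the Objective 2 result. Step 4 shows that it cannot unless that share shifts at the intervention, and nothing in the documents suggests that it does. A reader might also infer that reduced use should be concluded only when total dose falls. That has the opposite bias: a child held at constant dose per kg from 20 to 22 kg has a 10% higher total dose, so a within-patient requirement would hide real per-kg reductions in growing children.

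**Conclusion.** The point holds, with limits. Every PERT dose outcome with a stated scale is per kg, so weight gain beyond that of controls would be read as less PERT at unchanged intake. With 3-5% extra gain and an SD of 10-20%, P(decrease) moves from 50% to 56-69%; the continuous outcome moves by 2.9-4.8%. Both the gain and the SD are assumptions. The documents establish the mechanism, but not that it will operate or how strongly.

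The never-user problem is smaller. In Objective 2 a stable share attenuates the absolute effect, to 85% of its size at 15% non-users, and creates no false level or slope change. In Objective 3's binary comparison, unequal shares could bias the result in either direction, provided never-users are coded as no decrease, which the plan does not settle.

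This should be corrected before analysis. It does not invalidate the user/non-user outcome or the use of dose per kg.

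**What to change.** - In both arms, restrict dose-change outcomes to patients recorded on PERT in the last pre-index year, using the matching year as index for controls. Keep non-users in the user/non-user outcome.
- Add log total daily PERT dose as a continuous outcome beside dose per kg, compared with matched controls and adjusted for baseline dose, pre-exposure weight and age. State how patients who stop PERT are handled, since the log of a zero dose is undefined.
- Report weight change by arm. Interpret a per-kg fall without a fall in total dose relative to controls as possibly due to weight.

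The cost is one extra model per registry and a smaller dose-analysis set. No new data items are needed if numeric dose and weight were supplied. Confirm this first, because the Study Design section requests PERT as dosage or usage, and accepts BMI as an alternative to height and weight.

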Trends in the registries will be described, however no statistical tests will be used to directly similarities and differences between the registries over time due to the distinctions between the two registries.

2. The patient demographics lists above will be used for demographic propensity matched controls
 - Patient-level data will be used to create registry-based control groups with similar demographic features to those taking CFTR modulators. Due to the restricted genotype eligibility criteria for the earliest CFTR modulator, Ivacaftor, the CFTR user group may have distinct features compared to the overall registry. In addition the restrictive indications for the use of Ivacaftor and limited number of DIOS events on the registry will therefore mean the number of events within exposed individuals may be low. Therefore propensity scores will be used to define a control group of non-eligible non-users that are otherwise representative at the year CFTR modulator exposure was commenced. See directed acyclic graph (DAG) below.
 - Nearest neighbour matching, caliper 0.2 standard deviation, 3:1 ratio of unexposed to exposed will be used for propensity matching. Matching will be performed according to first year of exposure using all pre-exposure information in wide format. Standardised mean difference will be used to check covariate balance between matched and unmatched populations. Average treatment effect of treated will be used to assess matching specification with alternates.

Directed acyclic graph (DAG) for the potential relationship of CFTR modulator and DIOS

Objective 2: Determine the effect of CFTR modulators on DIOS and PERT, using an population-level controlled interrupted time series

This protocol is confidential and the property of the University of Nottingham. No part of it may be transmitted, reproduced, published, or used by others persons without prior written authorisation from the University of Nottingham

Objective 2 will investigate the effect of CFTR modulator intervention on the rate on PERT use and DIOS incidence.

We will test the hypotheses that;

- a) Ivacaftor introduction (2012) in patients with gating mutations lowered the rate of PERT use and the incidence of DIOS in both registries, and that
- b) The introduction of Orkambi (Ivacaftor/Lumacaftor) for those homozygous for F508del mutations in the US (2015) lowered the rate of PERT use and the incidence of DIOS. Specifically, we hypothesise a downward trend, no lag.

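### Hypothesis 2a fits one 2012 break to users who start in different years and gives its six-month rule no unit, so its slope cannot be read as the shape of the effect in users

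*Combined protocol and SAP*

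**What the plan says.** All of this is under STATISTICAL ANALYSIS unless stated otherwise.

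- **Hypothesis.** Objective 2 states 2a as "Ivacaftor introduction (2012) in patients with gating mutations lowered the rate of PERT use and the incidence of DIOS in both registries". That is a statement about introduction in an eligible genotype.
- **Population.** The series is described differently: "ITS will explore proportion of DIOS events at population level in the CFTR modulator population and the propensity score defined comparator population". Objective 1, item 2 matches controls by the user's first year of exposure, so the plan itself expects start years to differ.
- **Break and segments.** Both registries use the same split, for the UK "UK 2007-2011:2012-2017". The segments are labelled "Pre intervention: no CFTR modulator (time control" and "Post intervention: ivacaftor (minimum 6 months". The plan does not say whether the six months select patients or patient-years.
- **Model.** "Model includes: pre intervention, level change, post intervention: interaction with covariates (age, gender, disease status", with "Segmented regression (with and without lag term), and Prais-Winsten regression for serial correlation". The expected shape is "Impact model: downward trend (no/minimal level change". Distributed lags of one to three years are a sensitivity analysis.
- **Objective 3.** Leaving out the start year appears only among the sensitivity analyses, so by implication the main model keeps it. Yet section 4.2.2 says that DIOS cannot be ordered against drug start within a year. Its remedy removes patients with a single year of data, not start-year records.

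**The concern.** When users start in different years, a break at 2012 mixes two things: how fast the drug was taken up and what it did once taken. A drug that works at once but is taken up slowly produces a gradual fall in the users' series. The stated impact model is a claim about shape, and uptake alone can produce that shape. The secondary objective uses these results to form hypotheses about newer modulators, so a misread shape would carry forward.

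The missing unit of the six-month rule decides which problem arises. If it selects patients, years after 2012 but before the user's start sit in the post segment. If it selects patient-years, those years leave, and the post segment holds a different mix of patients each year.

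In Objective 3 the start-year record contains unexposed time and pulls the rate ratio toward 1.

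**Working it through.** The plan gives no sample size, power or uptake figure, so there is nothing of its own to reproduce. The checks below are noise-free and rest on assumptions.

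**Assumptions.** Start shares for 2012–2017: all in 2012; fast .6/.3/.1; mid .3/.4/.2/.1; late .1/.3/.3/.2/.1; even 1/6 each. Starts are uniform within the year. The true effect in users is an immediate step with no slope.

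**1. Patient reading (all of a user's years stay).** Exposed share in a year = earlier starters + 0.5 × that year's starters. For fast: 0.30, 0.75, 0.95, 1, 1, 1. The model fits the two segments separately and the pre segment is flat. So the slope is the least-squares slope of the six post values, 2.15/17.5 = 0.123 of the step per year, and the level is 0.833 − 2.5 × 0.123 = 0.53 of the step.

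**2. Patient-year reading (at least six months on drug in the year).** Half of that year's starters qualify, with mean exposure 0.75. Value = (earlier + 0.5 × new × 0.75)/(earlier + 0.5 × new). For fast: 0.75, 0.95, 0.987, 1, 1, 1, giving level 0.85 and slope 0.04.

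| | all 2012 | fast | mid | late | even |
|---|---|---|---|---|---|
| Post user-years before start year | 0% | 8% | 18% | 32% | 42% |
| Patient reading: step kept as level | 74% | 53% | 31% | 9% | 8% |
| Patient reading: slope, % of step per year | 7 | 12 | 17 | 20 | 17 |
| Patient-year reading: step kept as level | 87% | 85% | 82% | 79% | 83% |
| Lags 0–3, no post-slope: step recovered | 100% | 100% | 95% | 80% | 56% |
| Lags 0–3 with post-slope: step recovered | 100% | 100% | 88% | 52% | 8% |

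An example on the DIOS scale uses the UK 2019 figure of 5.7% as baseline. A 2.0-point step with uptake 10/40/20/15/10/5% fits as level −0.26 and slope −0.38 points per year. A gradual fall of 0.4 points per year, with everyone starting on 1 January 2012, fits as −0.20 and −0.40. The model can hardly tell them apart.

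**3. No drug effect.** Under the patient reading with a linear trend the fit returns level 0 and slope 0. Under the patient-year reading, assume baseline risk of 100 for 2012 starters and 10 more per later start year. For fast, the pre-period mean is 100 + 0.3 × 10 + 0.1 × 20 = 105, and the post values are 100, 102, 104.2, 105, 105, 105. The fitted level is 101.05 − 105 = −3.95, or −4% of baseline. Mid, late and even give −8%, −14% and −21%. All four have a rising slope.

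**4. Own-start time, start year dropped.** With a step of −30 and a common trend of −2 per year, users alone give −30.7 to −31.2 for staggered starts. Differencing against matched controls gives −30 and slope 0 in all five patterns, by construction if controls share the trend. A linear calendar-year term gives −30 for staggered starts. If the trend also curves by −0.2 per year squared, it gives −32.6 to −33.6.

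**5. Objective 3, true rate ratio 0.50.** With half the start year unexposed, that record's ratio is 1 − 0.5 × 0.5 = 0.75. Over k records per user the pooled ratio is [0.75 + 0.5(k − 1)]/k:
- ivacaftor, k = 6.0 to 3.5 across the five patterns: 0.54 to 0.57
- lumacaftor/ivacaftor against no modulator, k = 3 or 2: 0.58 or 0.63

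Under a six-month patient-year rule, half the start-year records stay, each with ratio 0.625. The ivacaftor figure is then [0.5 × 0.625 + 0.5(k − 1)]/(k − 0.5) = 0.51 to 0.52.

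**6. Precision.** SE² of the log ratio = 1/exposed events + 1/control events, with 3:1 controls losing the same record. In units of the control rate, k = 6 gives 1/3.25 + 1/18 = 0.363 with the record and 1/2.5 + 1/15 = 0.467 without it. The SE ratio is √(0.467/0.363) = 1.13. At k = 3.5 it is 1.25. Log ratio divided by SE stays at about 99–100% of the inclusive value. For three or two records the SE rises 31% or 55%, and that ratio stays at 98% or 95%.

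**The case against.** The strongest reply is that 2a asks about introduction at population level, that a 2012 break answers this, and that Objective 3 supplies the patient-level view. The first part stands: the break is a legitimate introduction analysis and should be kept. But the series is defined on users rather than on the eligible genotype, and the impact model invites a reading of shape.

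The segment labels lean toward patient-years, under which most of the step stays as level. That is fair, but the plan does not say so, and that reading changes the patient mix. Without the not-yet-exposed years, the series no longer estimates introduction cleanly either.

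The planned lags help when uptake is early. They stay on the calendar axis and recover much less when uptake is late, above all with a post-intervention slope in the model. Prais-Winsten addresses serial correlation, not start timing.

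For Objective 3, start-year exclusion, lags and cumulative exposure are already planned, and a six-month patient-year rule would leave little to gain for ivacaftor. Both points stand, and they keep this minor.

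A reader might infer that the 2012 break manufactures an effect. The documents do not support that. With all of a user's years kept and a linear trend, no effect returns zero. The spurious level in step 3 needs the patient-year reading and a risk gradient by start year, which is assumed here and appears nowhere in the documents. Controls that enter by the same index-year rule could remove it.

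**Conclusion.** The point holds as a minor, cheap improvement. The text establishes a single 2012 break, a series of users with differing start years, a six-month rule without a unit, and a start-year record kept in Objective 3 by implication.

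The sizes rest on assumed uptake, starts spread evenly within the year and a pure step. The loss of shape is large under the patient reading, except where uptake is early, and mild under the patient-year reading. Only the mid, late and even patterns resemble a trend with little level change. The slope in 2a can therefore be reported as uptake and drug effect combined, but not as the time course in users.

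In Objective 3 the bias is toward no effect and modest for ivacaftor. It is larger only in the secondary lumacaftor/ivacaftor comparison. Neither part invalidates the study.

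**What to change.** 1. **Introduction analysis.** Keep the 2012-break model with its lags, in a stated fixed cohort: either the eligible genotype or all users with all their years. Do not apply the six-month rule to patient-years here. Say that the slope combines uptake and drug effect.
2. **Effect in users.** Add an event-time analysis. Index each user and the matched controls to the user's first exposure year, drop that year for both, and difference against the controls. Do not rely on a linear calendar-year term alone.
3. **Objective 3.** Make the planned start-year exclusion primary and the inclusive model the sensitivity analysis. Drop the start-year record and the matched controls' record for the same year, not the patient. The exception is a registry whose DIOS timing resolves the order throughout. Decide this per registry, not per event, so that keeping a record does not depend on having had an event.

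**Cost.** SAP wording and a re-indexed dataset; start dates and any available DIOS timing are already on the request list under STUDY DESIGN. One record per exposed patient is lost, 2017 starters contribute no post record, and late event years are thin: event year 5 holds 60% of users under fast uptake and 10% under late. The SE of the log ratio rises 13–25% for ivacaftor at a true ratio of 0.50, with log ratio over SE almost unchanged. Exclusion therefore removes bias but gains no power, and Objective 1 already warns that events among the exposed may be few.
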